13. Female subjects of childbearing potential should have a negative urine or serum pregnancy within 72 hours prior to receiving the first dose of study medication. If the urine test is positive or cannot be confirmed as negative, a serum pregnancy test will be required.
14. Female subjects of childbearing potential should be willing to use 1 method of highly effective birth control or be surgically sterile, or abstain from heterosexual activity for the course of the study through 180 days after the last dose of study medication (Reference Section 8.1). Subjects of childbearing potential are those who have not been surgically sterilized or have not been free from menses for > 1 year.
15. Male subjects should agree to use an adequate method of contraception starting with the first dose of study therapy through 180 days after the last dose of study therapy.
16. Patient is \geq 5 years free of another primary malignancy, except: a) if the other malignancy is basal cell carcinoma or cervical carcinoma in situ or b) if the other primary malignancy is not considered clinically significant and is requiring no active intervention

4.5 Exclusion Criteria:

The subject **must be excluded** from participating in the trial if the subject:

1. Is currently participating in or has participated in a study of an investigational agent or using an investigational device within 4 weeks of the first dose of treatment.
2. Has a target lesion/s for SBRT that demonstrate any of the following:
 - a. located within 2 cm of the proximal bronchial tree
 - b. > 5 cm (> 50 cc) in greatest dimension
3. Has a target lesion/s in a region that previously received high dose RT (>50 Gy) demonstrating any of the following:
 - a. carotid artery encasement (> 180 degrees)

- b. unprotected carotid artery (i.e. skin is directly over the carotid without intervening soft tissue, especially after prior neck dissection without a vascularized free flap) (a&b due to risk of carotid blow out)
 - c. skin infiltration by tumor (due to risk of fistula)
 - d. located in the larynx/hypopharynx primaries (due airway threat)
 - e. treated with high dose radiation therapy (>50 Gy) within 6 months or less of trial enrollment
4. Prior receipt of an anti-PD-1, anti-PDL1 or anti-CTLA4 immune checkpoint inhibitor.
5. Current or prior use of immunosuppressive medication within 14 days before the first dose of nivolumab or ipilimumab. The following are exceptions to this criterion:

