5.2.3 Treatment planning, dose fractionation and specification

Computer based planning & QA will be performed using our standard institutional SBRT guidelines, including corrections for tissue heterogeneity, and robustness analysis (for Proton therapy). Treatment planning may be done with IMRT, VMAT, Proton beam RT (Pencil beam RT or Uniform scanning).

The dose prescription will be as follows: 24 Gy given in 3 fractions to PTV (80-95% IDL) delivered at 8 Gy per fraction every other day.

Dose rate: For the purpose of this study, dose rate utilized will be that which is commissioned by the manufacturer and the medical physics group for external beam radiotherapy delivery by the treating institution. There will be no special dose rate modifications required for this study.

The following PRV dose constraints will be used: (adopted from Timmerman RD. An overview of hypofractionation. Seminars of Radiation Oncology 2008 Oct;18(4):215-222).

Spinal cord max 21Gy, 18Gy (< 0.35cc), 12 Gy (<1cc)

Brain stem max 23 Gy, 18 Gy (< 0.5cc)

Optic chiasm max 15 Gy, 12 Gy (< 0.2cc) (for bilateral blindness risk)

Ipsilateral Optic nerve max 18 Gy, 15 Gy (< 0.2cc)

Contralateral optic nerve max 12 Gy, 10 Gy (< 0.5cc)

Carotid artery max 15 Gy, (V12 Gy to < 30% of carotid volume)

Brachial plexus max 24 Gy, 20 Gy (< 3cc)

Esophagus* max 24 Gy, 17 Gy (< 5cc)

Heart/Pericardium max 24 Gy, 20 Gy (< 15cc)

Trachea* max 24 Gy, 15 Gy (< 4cc)

Bronchus max 23 Gy, 18 Gy (< 1cc)

Ribs max 24 Gy, 20 Gy (< 5cc)

Skin 24 Gy (< 10cc), 20 Gy (<10cc)

Lung (Right & Left) – Volume to spare > 1000cc to </= 12 Gy and
> 1500 cc to </= 11.5 Gy, V15 Gy < 35%

Liver – spare >700cc to </=19 Gy

Stomach – max 22 Gy, 16 Gy to < 10cc

Rest of OARS = ALARA

* avoid circumferential radiation

Three-dimensional coplanar or non-coplanar beam arrangements will be custom designed for each case to deliver highly conformal prescription dose distributions. Non-opposing, noncoplanar beams are preferable. Typically, ≥ 10 beams of radiation will be used with roughly equal weighting for photon planning. Generally, more beams are used for larger lesion sizes. When static beams are used, a minimum of 7 non-opposing beams should be used. For arc rotation techniques, a minimum of 340 degrees (cumulative for all beams) should be utilized. For arc rotation techniques, a minimum of 340 degrees (cumulative for all beams) should be utilized.

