^c To be done on each visit prior to administration of investigational drug. Concomitant medication collected up to the Safety Follow (-30 days post last dose of study treatment) or initiation of new anti-cancer treatment. AEs will be collected up to 100 days post last dose of study treatment or initiation of new anti-cancer treatment.

^d On weeks 1-24, see Section 5.1.1 for Nivolumab administration (-2/+3days), **nivolumab doses are given at least 12 days apart**

^e On weeks 25-52, see Section 5.1.1 for Nivolumab administration(-2/+3days) at a flat dose of 480mg, **nivolumab doses are given at least 12 days apart**

^f On weeks 1-24, see Section 5.1.1 for Ipilimumab administration(-2/+3 days) for 3 doses

^g XRT to begin 2 weeks after the first dose of Nivolumab and Ipilimumab and to be completed in 2 weeks

^h Add free T4 if TSH is abnormal. Repeat at least every 12 weeks.

ⁱ If screening laboratory assessments are performed within 3 days prior to Day 1 they do not need to be repeated at Day 1. Results for safety blood test must be available and reviewed before commencing an infusion. **During weeks 7-24:** CBC and serum chemistries will be done every 2 weeks prior to the nivolumab or nivolumab/ipilimumab infusions. **During weeks 25-52:** CBC and serum chemistries will be performed every 4 weeks prior to each nivolumab infusion.

^j Urinalysis performed at Screening and then as clinically indicated.

^k Coagulation tests: prothrombin time, aPTT and INR – only performed at Screening and then as clinically indicated.

^l Correlative blood samples will be collected on 3 occasions, prior to week 1, prior to week 8 and prior to week 16.

^m Timing of CT scans for tumor assessments will be every 8 weeks (+/- 7 days).

ⁿ If a subject initiates a new anti-cancer therapy within 30 days after the last dose of trial treatment, the 30 day Safety Follow-up visit must occur before the first dose of the new therapy. Once new anti-cancer therapy has been initiated the subject will move into survival follow-up.

^o Follow-up phase for patients that discontinue treatment for reasons other than disease progression (see Section 7.1.4.5).

^p Patients that have documented disease progression or starts treatment on new anti-cancer therapy will move into the survival follow-up phase.

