7.1.2 Clinical Procedures/Assessments

7.1.2.1 Adverse Event (AE) Monitoring

The investigator or qualified designee will assess each subject to evaluate for potential new or worsening AEs as specified in the Schedule of Assessments (Section 7) and more frequently if clinically indicated. Adverse experiences will be graded and recorded throughout the study and during the follow-up period according to NCI CTCAE Version 5.0 (see Sections: 5.1.2, 8.2, 8.3). Toxicities will be characterized in terms regarding seriousness, causality, toxicity grading, and action taken with regard to trial treatment. AE collection will start once the subject signs consent and up to 100 days after the last dose of study treatment.

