7.1.4.3 End of Treatment Visit

- Targeted physical examination
- Vital Signs and weight
- ECOG performance status
- Adverse event review/serious adverse event review
- Concomitant medication review

7.1.4.4 30-Day Post Last Treatment Visit

- Targeted physical examination
- Vital Signs and weight
- ECOG performance status
- Adverse event/serious adverse event review
- Concomitant medication review

7.1.4.5 Long-Term Follow-Up Visits every 8 weeks (\pm 7 days) for patients without documented progression/ have not started new anti-cancer therapy

- ECOG performance status
- Adverse event/serious adverse event review collection up to 100 days after last dose of study treatment
- Follow-up will continue until end of study

7.1.4.6 Survival Follow-Up -Every 12 weeks for patients with documented disease progression/have started new anti-cancer therapy

- Medical record confirmation or phone contact confirmation to document survival

- Adverse event/serious adverse event review collection up to 100 days after last dose of study treatment
- Follow-up will continue until end of study.

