8. SAFETY AND REPORTING

All Serious Adverse Events (SAEs) that occur following the subject's written consent to participate in the study through 100 days of last dose of study treatment must be reported to BMS Worldwide Safety, whether related or not related to study drug. If applicable, SAEs must be collected that relate to any later protocol-specified procedure (e.g., a follow-up skin biopsy). Hospitalizations and/or death related solely to progression of the underlying disease will not be considered an SAE.

Following the subject's written consent to participate in the study, all SAEs, whether related or not related to study drug, are collected, including those thought to be associated with protocol-specified procedures. The investigator should report any SAE occurring after these aforementioned time periods, which is believed to be related to study drug or protocol-specified procedure.

An SAE report should be completed for any event where doubt exists regarding its seriousness;

If the investigator believes that an SAE is not related to study drug, but is potentially related to the conditions of the study (such as withdrawal of previous therapy or a complication of a study procedure), the relationship should be specified in the narrative section of the SAE Report Form.

An appropriate SAE form (e.g. ex-US = CIOMS form or USA = Medwatch form) should be used to report SAEs to BMS. The BMS protocol ID number must be included on whatever form is submitted by the Sponsor/Investigator.

- The CIOMS form is available at: <http://www.cioms.ch/index.php/cioms-form-i>
- The MedWatch form is available at:
<https://www.fda.gov/downloads/AboutFDA/ReportsManualsForms/Forms/UCM048334.pdf>
- [name]
- In accordance with local regulations, BMS will notify investigators of all reported SAEs that are suspected (related to the investigational product) and unexpected (i.e., not previously described in the IB). An event meeting these criteria is termed a Suspected, Unexpected Serious Adverse Reaction (SUSAR). Investigator notification of these events will be in the form of a SUSAR Report.

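### Adverse-event collection runs 100 days from the last dose with no clock from SBRT, so patients who stop drugs early are observed least for late radiation injury

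*Combined protocol and SAP*

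**What the plan says.** Four places set the adverse-event (AE) window, all from the last dose:

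- Section 7, footnote c: "AEs will be collected up to 100 days post last dose of study treatment", with the start of new anti-cancer treatment as an alternative end.
- Section 7.1.2.1: "AE collection will start once the subject signs consent and up to 100 days after the last dose of study treatment".
- Sections 7.1.4.5 (long-term follow-up) and 7.1.4.6 (survival follow-up): "Adverse event/serious adverse event review collection up to 100 days after last dose of study treatment".

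Contact with the patient does not stop there. Both follow-up sections say "Follow-up will continue until end of study", every 8 weeks without progression or new therapy and every 12 weeks otherwise. Once AE review has closed, the first lists only ECOG status and the second only confirmation of survival.

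SBRT starts two weeks after the first drug doses: three fractions, every other day (synopsis, Study Design; footnote g). Drug dosing can run to about one year (Section 5.1.1). Section 5.1.2 counts radiation toxicity among the AEs monitored but gives it no window of its own.

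The synopsis Statistical Plan summarizes toxicity as the number and percentage of patients. Statistical Considerations takes all enrolled patients as the safety population.

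**The concern.** The primary objective is the safety of the three-part combination, and the run-in exists because radiation had not been studied with these two drugs. The protocol itself names severe radiation injuries. For previously irradiated regions, Section 4.5 item 3 gives its reasons as "a&b due to risk of carotid blow out" and also mentions fistula and airway threat. Section 5.2.3 annotates one dose constraint "for bilateral blindness risk".

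Radiation exposure is complete by about week 3 or 4, yet the time during which a new radiation injury would be recorded is set by the drug schedule. A crude percentage then pools patients with very different observation times. The shorter times belong to patients who came off drug early, so length of observation is linked to clinical course. An injury that first appears after the window tends to go unrecorded, which pushes the late-safety result toward looking favourable.

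**Working it through.** The plan gives no figure for radiation follow-up, so there is none to reproduce. The check is calendar arithmetic, followed by a rough look at its scale.

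**Inputs.** Day 1 is the first drug dose. Week w begins on day 7(w − 1) + 1. Fractions every other day from day 15 fall on days 15, 17 and 19 (synopsis). Nivolumab is given every 2 weeks for 12 doses (weeks 1 to 23), then every 4 weeks from week 25 (Section 5.1.1), which gives weeks 25, 29, 33, 37, 41, 45 and 49.

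**Formula.** Days observed after the last fraction = (last dose day + 100) − 19. If SBRT itself counts as study treatment, the last dose day is the later of the last infusion and day 19.

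| Last drug dose | Day | AE review closes | Days after last fraction |
|---|---|---|---|
| Week 1 | 1 | 101 | 82 (100 if SBRT counts) |
| Week 3 | 15 | 115 | 96 (100 if SBRT counts) |
| Week 13 | 85 | 185 | 166 |
| Week 23 | 155 | 255 | 236 |
| Week 49 | 337 | 437 | 418 |

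From a week-3 stop to a week-49 finish, the ratio is 418/100 = 4.2 to 418/96 = 4.4.

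**Sensitivity.** Footnote g allows two weeks for SBRT. With the last fraction on day 28, a week-1 stop gives 101 − 28 = 73 days and a week-49 finish 437 − 28 = 409. Section 5.1.1 allows up to 8 four-weekly doses; an eighth would fall in week 53 (day 365), giving 465 − 19 = 446 days. The pattern does not change.

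**Effect on the sized estimate.** The sample size rests on acute drug-related Grade 3 or higher toxicity: 1.96 × √(0.3 × 0.7/20) = 0.201, which matches the stated 20 points. The protocol reviews acute toxicity over 12 weeks, to day 84. Even a patient given only the week-1 dose is covered to day 101, so all surviving patients are covered through day 84 unless new therapy closes collection sooner.

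**Scale of the late gap (model, not data).** Assumptions: exponential times with the Introduction's medians for earlier regimens (PFS 5 to 6 months, OS 12 to 14 months), drugs stopped at progression or after week 49, 24 months of follow-up, and no closure for new therapy. The share of post-SBRT time alive without scheduled AE collection is about 38% if progression and death times are perfectly correlated and about 51% if they are independent. Beyond 6 months after SBRT, the range is about 60% to 78%. The documents do not give that dependence, so only the range can be stated.

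**The case against.** **The primary result might seem untouched.** The only estimate with a stated precision is acute and drug-related, and every window spans the 12-week review. That stands: a reader might infer from the fourfold difference that the primary toxicity rate is biased, and the documents do not support this for the acute rate. What remains exposed is late radiation toxicity in the crude tables and in the conclusion that the combination is safe and well tolerated.

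**Stopping for toxicity does not hide a case.** A patient who stopped because of a Grade 3 or higher event is already counted in a patient-level Grade 3 or higher rate. This also stands. The loss falls mainly on those who stopped for progression, withdrawal or lower-grade events, so the driver is how long drugs were continued, not how well they were tolerated.

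**Other passages seem to keep collection open.** The schedule grid marks AE assessment in both follow-up columns, but footnote c limits that row. Sections 4.3 and 7.1.2.1 speak of monitoring throughout the trial or study, yet 7.1.2.1 ends with the 100-day limit. Section 5.1.3.3 promises safety follow-up after discontinuation without a duration. Section 8.3 makes 100 days a floor for non-serious events, but sets no longer period. Following events to resolution helps only those already recorded.

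**The feared injuries would usually be serious.** Section 8 says "The investigator should report any SAE occurring after these aforementioned time periods", provided it is believed related to study drug or a protocol-specified procedure. It would therefore be wrong to infer that nothing can be captured after day 100. But this route is unsolicited, depends on the investigator's causality judgement, and does not say whether SBRT is such a procedure. A new non-serious Grade 3 event has no scheduled collection.

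**Conclusion.** The point holds as a gap in late-safety ascertainment. Scheduled observation after the last fraction runs from about 96 to 100 days (drugs stopped at week 3) to about 418 days (last infusion in week 49). That result needs only the planned calendar. The direction is under-counting of late radiation injury in patients who left drug treatment early.

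The number of missed events cannot be stated. The documents give no late-injury rate, and the modelled shares of time (about 38% to 51% overall, 60% to 78% beyond 6 months) depend on the assumptions listed. A reader might take them as shares of events missed. That would require a constant injury hazard and no capture at all after closure; the first has no basis in the documents, and the second conflicts with Section 8. With 20 patients the absolute number may be small. The change is worth making because it costs little and the information is hard to recover later.

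**What to change.** 1. Keep 100 days for drug toxicity. In footnote c and Sections 7.1.2.1, 7.1.4.5 and 7.1.4.6, add that Grade 3 or higher toxicity at irradiated sites is asked about and recorded at each follow-up contact already scheduled until end of study, with events after new anti-cancer therapy flagged.
2. Report these events with time from the first SBRT fraction and each patient's length of follow-up, beside the crude percentage. Cumulative incidence with death as a competing event is optional with 20 patients.
3. State whether SBRT counts as study treatment and as a protocol-specified procedure.
4. Reconcile the 100-day ceiling in Section 7 and its subsections with the 100-day minimum in Section 8.3. Reconcile footnote c, which closes collection at new therapy, with Section 7.1.4.6, which continues AE review to 100 days in such patients. Reconcile the one-week SBRT course in the synopsis with the two weeks in footnote g.

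**Cost.** Amendment wording, a case report form field and one question at existing contacts; no new visits or patients. Attribution will be less certain after new therapy, and the reported late-toxicity rate may be less favourable.

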7.1 Trial Procedures

7.1.1 Administrative

The Schedule of Assessments chart- Section 7 summarizes the trial procedures to be performed at each visit. Individual trial procedures are described in detail below. It may be necessary to perform these procedures at unscheduled time points if deemed clinically necessary by the investigator and/or Sponsor.

7.1.1.1 Informed Consent

The approved informed consent form will adhere to the ethical principles that have their origin in the Declaration of Helsinki. Investigator obtaining consent must ensure that subjects--or, in those situations where consent cannot be given by subjects, their legally acceptable representatives--are clearly and fully informed about the purpose, potential risks, and other critical issues regarding clinical studies in which they volunteer to participate. Consent must be documented by the subject's dated signature or by the subject's legally acceptable representative's dated signature on a consent form along with the dated signature of the person conducting the consent discussion.

A copy of the signed and dated consent form should be given to the subject before participation in the trial. The initial informed consent form, any subsequent revised written informed consent form and any written information provided to the subject must receive the IRB/ERC's approval/favorable opinion in advance of use.

The subject or his/her legally acceptable representative should be informed in a timely manner if new information becomes available that may be relevant to the subject's willingness to continue participation in the trial. The communication of this information will be provided and documented via a revised consent form or addendum to the original consent form that captures the subject's dated signature or by the subject's legally acceptable representative's dated signature.

The informed consent will adhere to IRB/ERC requirements, applicable laws and regulations and Sponsor requirements.

7.1.1.2 Inclusion/Exclusion Criteria

All inclusion and exclusion criteria will be reviewed by the investigator or qualified designee to ensure that the subject qualifies for the trial.

7.1.1.3 Medical History

A medical history will be obtained by the investigator or qualified designee. Medical history will include all active conditions, and any condition diagnosed within the prior 10 years that are considered to be clinically significant by the Investigator. Details regarding the disease for which the subject has enrolled in this study will be recorded separately and not listed as medical history.

7.1.1.4 Prior and Concomitant Medications Review

The investigator or qualified designee will review prior medication use, including any protocol-specified washout requirement, and record prior medication taken by the subject within 28 days before starting the trial. Treatment for the disease for which the subject has enrolled in this study will be recorded separately and not listed as a prior medication.

7.1.1.5 Disease Detail, Treatments and Subsequent Anti-Cancer Therapy

The investigator or qualified designee will obtain prior and current details regarding disease status. The investigator or qualified designee will review all prior cancer treatments including systemic treatments, radiation and surgeries.

The investigator or qualified designee will review all new anti-neoplastic therapy initiated after the last dose of trial treatment. If a subject initiates a new anti-cancer therapy within 30 days after the last dose of trial treatment, the 30 day Safety Follow-up visit must occur before the first dose of the new therapy. Once new anti-cancer therapy has been initiated the subject will move into survival follow-up.

